3.4.2. Virologic Response-Based Treatment Stopping Criteria

The following on-treatment Virologic Response-based Treatment Stopping Criteria will be utilized:

- Confirmed HCV RNA ≥ LLOQ after 2 consecutive HCV RNA < LLOQ
- Confirmed > 1 log₁₀ increase in HCV RNA from nadir
- HCV RNA \geq LLOQ through 8 weeks of treatment

Confirmation, when required, should be performed as soon as possible and must occur no later than 2 weeks after an initial observation indicating virologic failure during the on-treatment phase.

Subjects who terminate study drug early due to virologic failure as defined above will complete the Early Termination (ET) visit and all posttreatment visits.

4. SUBJECT POPULATION

4.1. Number of Subjects and Subject Selection

Approximately 36 chronic HCV infected male and non-pregnant female subjects, ages 18 or older, with compensated cirrhosis at Screening will be enrolled in this study.

In order to manage the total study enrollment, Gilead Sciences, Inc., at its sole discretion, may suspend screening and/or enrollment at any site or study-wide at any time.

4.2. Inclusion Criteria

Subjects must meet all of the following inclusion criteria to be eligible for participation in this study.

- 1) Willing and able to give informed consent prior to any study specific procedures being performed. If subject is a minor, legal representative will provide consent.
- 2) Male or female, age \geq 18 years at Screening
- 3) Body weight \geq 40 kg at Screening
- 4) Quantifiable HCV RNA (≥ lower limit of quantitation [LLOQ]) at Screening
- 5) Chronic HCV infection (≥ 6 months prior to Screening) documented by prior medical history or liver biopsy.
- 6) Confirmation of cirrhosis by any one of the following methods:
 - a) Liver biopsy showing cirrhosis (eg, Metavir score = 4 or Ishak score ≥ 5)
 - b) Fibroscan within 4 months of Day 1 showing cirrhosis or results > 12.5 kPa
 - c) FibroTest® score of > 0.75 at Screening (only in the absence of liver biopsy or availability of Fibroscan)
- 7) HCV treatment status defined as one of the following, and with medical records that include sufficient detail to allow for categorization as follows:
 - a) HCV treatment-naive: Subject has had no prior exposure to any IFN, RBV, or other approved or experimental HCV-specific direct-acting antiviral agents.
 - b) HCV treatment-experienced: Subject has had prior treatment with an approved or experimental IFN-containing regimen with or without NS3/4A protease inhibitors. Note: See Exclusion Criterion #5: if treatment-experienced, prior exposure to any direct-acting antiviral agent targeting the HCV NS5A or NS5B is prohibited.

- 8) If treatment-experienced, the most recent HCV treatment must have completed at least 8 weeks prior to Screening
- 9) Liver imaging (eg, ultrasound or CT scan, at the discretion of the investigator) performed within 4 months of Day 1 to exclude hepatocellular carcinoma (HCC)
- 10) Females of childbearing potential (as defined in Appendix 4) must have a negative serum pregnancy test at Screening and a negative urine pregnancy test on Day 1 prior to enrollment.
- 11) Male subjects and female subjects of childbearing potential who engage in heterosexual intercourse must agree to use protocol specified method(s) of contraception as described in Appendix 4.
- 12) Male subjects must agree and refrain from sperm donation during treatment and until at least 30 days after the last dose SOF/VEL FDC. Female subjects must also refrain from egg donation and in vitro fertilization during treatment and until at least 30 days after the last dose of SOF/VEL FDC.
- 13) Lactating females must agree to discontinue nursing before the study drug is administered and through at least 30 days after the last dose of study drug.
- 14) Subject must be of generally good health, with the exception of chronic HCV infection, as determined by the investigator.
- 15) Subject must be able to comply with the dosing instructions for study drug administration and able to complete the study schedule of assessments, including all required posttreatment visits.

4.3. Exclusion Criteria

Subjects who meet *any* of the following exclusion criteria are not to be enrolled in this study.

- 1) Current or prior history of any of the following:
 - a) Clinically significant illness or currently under evaluation for a potentially clinically significant illness (other than HCV) or any other major medical disorder that may interfere with subject treatment, assessment, or compliance with the protocol
 - b) Gastrointestinal disorder or postoperative condition that could interfere with the absorption of the study drug
 - c) Difficulty with blood collection and/or poor venous access for the purposes of phlebotomy
 - d) Any current or past clinical evidence of decompensated liver disease (eg, ascites, hepatic encephalopathy, or variceal bleeding).
 - e) Solid organ transplantation

- f) Significant pulmonary disease
- g) Unstable cardiac disease or significant cardiac event within one year prior to Screening
- h) Porphyria
- i) History of clinically significant hemoglobinopathy (eg, sickle cell disease, thalassemia)
- j) Psychiatric hospitalization, suicide attempt and/or a period of disability as a result of their psychiatric illness within the last 2 years of Screening
- k) Malignancy within the 5 years prior to Screening with the exception of specific cancers that are cured by surgical resection (basal cell skin cancer, etc.). Subjects under evaluation for possible malignancy are not eligible
- 1) Prior or current hepatocellular carcinoma (HCC)
- m) Significant drug allergy (such as anaphylaxis or hepatotoxicity)
- 2) Infection with human immunodeficiency virus (HIV) at Screening
- 3) Hepatitis B virus (HBV) surface antigen positive at Screening
- 4) Screening ECG with clinically significant abnormalities
- 5) Prior exposure to any HCV NS5A or NS5B inhibitor
- 6) History of clinically significant medical condition associated with other chronic liver disease (eg, hemochromatosis, autoimmune hepatitis, Wilson's disease, α-1-antitrypsin deficiency, alcoholic liver disease, non-alcoholic steatohepatitis or toxin exposure)
- 7) Pregnant or nursing female or male with pregnant female partner
- 8) Women who wish to become pregnant or males with female partners who wish to become pregnant during study treatment and through 30 days after the last dose SOF/VEL FDC
- 9) Subjects with any of the following laboratory parameters at Screening:
 - a) ALT $> 10 \times$ upper limit of normal (ULN)
 - b) AST $> 10 \times ULN$
 - c) Direct bilirubin $> 1.5 \times ULN$
 - d) Platelets $< 50,000/\mu L$
 - e) HbA1c > 8.5%

- f) Hemoglobin < 10 g/dL
- g) Albumin < 3 g/dL
- h) International Normalized Ratio of prothrombin time (INR) $> 1.5 \times ULN$ unless subject has known hemophilia or is stable on an anticoagulant regimen affecting INR
- i) Neutrophil count < 500/μL
- 10) Use of any prohibited concomitant medications as described in Section 5.4 of the Protocol
- 11) Chronic use of systemically administered immunosuppressive agents (eg, prednisone equivalent > 10 mg/day)
- 12) Known hypersensitivity or contraindication to SOF, VEL, or the metabolites or formulation excipients

5. INVESTIGATIONAL MEDICINAL PRODUCTS

5.1. Randomization, Blinding and Treatment Codes

This is a multicenter, open-label study in subjects with chronic HCV infection with compensated cirrhosis. No blinding is required.

All subjects will be enrolled to receive SOF/VEL FDC for 12 weeks.

5.2. Description and Handling of SOF/VEL FDC

5.2.1. Formulation

The SOF/VEL FDC (400/100 mg) tablets are pink, diamond-shaped, film-coated tablets, debossed with "GSI" on one side and "7916" on the other side. In addition to the active ingredients, the SOF/VEL FDC tablets contain copovidone, microcrystalline cellulose, croscarmellose sodium, magnesium stearate, polyvinyl alcohol, titanium dioxide, polyethylene glycol, talc, and iron oxide red.

5.2.2. SOF/VEL FDC Packaging and Labeling

SOF/VEL FDC (400/100 mg) tablets are packaged in white, high density polyethylene (HDPE) bottles. Each bottle contains 28 tablets and polyester packing material. Each bottle is enclosed with a white, continuous thread, child-resistant polypropylene screw cap with an induction-sealed, aluminum-faced liner.

SOF/VEL FDC bottles to be distributed to centers in Japan shall be labeled for clinical use to meet applicable requirements of the J-GCP (Ministerial Ordinance on Good Clinical Practice for Drugs).

5.2.3. SOF/VEL FDC Storage and Handling

SOF/VEL FDC tablets should be stored below 30 °C (86 °F).

All drug products should be stored in a securely locked area, accessible only to authorized site personnel. To ensure the stability of the study drug and to ensure proper product identification, the drug product should not be stored in a container other than the container in which they are supplied. Consideration should be given to handling, preparation, and disposal through measures that minimize drug contact with the body. Appropriate precautions should be followed to avoid direct eye contact or exposure through inhalation when handling SOF/VEL FDC tablets.

5.3. Dosage and Administration of SOF/VEL FDC

SOF/VEL FDC tablet is to be administered once daily with or without food. Each subject must be given instructions to maintain approximately the same daily dosing interval between study drug doses.

If a subject does not take the SOF/VEL FDC dose at the usual time, it may be taken up to 18 hours later; however, no more than one tablet should be taken on any calendar day. The subject should resume the standing dosing schedule on the next day.

Study drug should not be cut or split. SOF/VEL FDC tablets will be provided by Gilead Sciences for all subjects.

5.4. Prior and Concomitant Medications

All concomitant medications taken within 30 days prior to Screening, up to and including 30 days after the last dose of study drug, need to be recorded in the source documents and electronic case report form (eCRF) (including all blood products).

Investigational agents or devices for any indication are prohibited from 28 days prior to the Day 1 visit through the end of study drug dosing.

Concomitant use of certain medications or herbal/natural supplements (such as moderate to potent inducers of drug transporters or metabolizing enzymes, eg, P-gp, CYP2B6, CYP2C8, or CYP3A) with the study drug may result in pharmacokinetic interactions resulting in increases or decreases in exposure of the study drug or these medications.

Investigators should refer to the product/package inserts of other medications for recommendations or contraindications related to their use.

Table 5-1 below contains examples of medications that are prohibited from 21 days prior to Day 1 through the end of treatment and those medications which may be used with caution. The use of amiodarone is prohibited from 60 days prior to Day 1 through the end of treatment.

Table 5-1. Disallowed and Concomitant Medications to be Used with Caution

Drug Class	Agents Disallowed	Use with Caution
Acid Reducing Agents ^a		Proton- Pump Inhibitors, H2-Receptor Antagonists, Antacids
Anticonvulsants ^b	Phenytoin, Carbamazepine, Phenobarbital	
Antimycobacterials ^b	Rifampicin	Rifabutin
Cardiac Medications ^c	Amiodarone ^d	Digoxin ^e
Herbal/Natural Supplements ^b	St. John's Wort	
HMG-CoA Reductase Inhibitors ^f		Rosuvastatin (≤10 mg/day), Atorvastatin
Other	Bosentan ^b , Modafinil ^b , Sulfasalazine ^c , Methotrexate ^c	Dabigatran etexilate ^g

a Proton pump inhibitor (PPI) doses comparable with omeprazole 20mg can be administered with SOF/VEL FDC when SOF/VEL FDC is administered with food and taken 4 hours before the PPI. H2-receptor antagonists must not exceed a dose of 40 mg famotidine or equivalent and can be taken simultaneously with SOF/VEL FDC and/or staggered by 12 hours. Antacids that directly neutralize stomach acid may not be taken within 4 hours (before or after) of SOF/VEL FDC administration.

- b May result in a decrease in the concentration of study drug.
- c May result in an increase in the concentration of study drug and/or concomitant medications.
- d May result in symptomatic bradycardia. Mechanism is not currently known. The use of amiodarone is prohibited from 60 days prior to Day 1 through the end of treatment.
- e Monitor for signs and symptoms of digoxin toxicity.
- f Use with SOF/VEL FDC may result in an increase in the concentration of HMG-CoA Reductase Inhibitors. Monitor for signs and symptoms of muscle weakness or myopathy, including rhabdomyolysis. Rosuvastatin may be coadministered at a dose that does not exceed 10 mg.
- g As dabigatran exposure may increase when coadministered with SOF/VEL FDC, clinical monitoring for signs of bleeding and anemia is recommended, in addition to monitoring patients using coagulation testing.

Medications for disease conditions **excluded** from the protocol (eg, HIV infection) are not listed under this Concomitant Medication section and are disallowed in the study.

Should subjects have a need to initiate treatment with any excluded concomitant medication, the Medical Monitor must be consulted prior to initiation of the new medication. In instances where an excluded medication is initiated prior to discussion with the Sponsor, the Investigator must notify Gilead as soon as he/she is aware of the use of the excluded medication.

5.5. Study Drug Adherence and Accountability for SOF/VEL FDC

The investigator or designee (ie pharmacist) is responsible for ensuring adequate accountability of all used and unused study drug. This includes acknowledgement of receipt of each shipment of study drug (quantity and condition). All used and unused study drug dispensed to subjects must be returned to the site.

SOF/VEL FDC accountability records will be provided to each study site to:

- Record the lot number, expiration date (if necessary)
- Record the date received and quantity of study drug kits
- Record the date, subject number and the study drug kit number dispensed
- Record the date, quantity of used and unused IMP returned, along with the initials of the person recording the information.

5.5.1. Investigational Medicinal Product Return or Disposal

Refer to Section 9.1.8 for information on return and disposal of study drug.

6. STUDY PROCEDURES

The study procedures to be conducted for each subject enrolled in the study are presented in tabular form in Appendix 2 and described in the text that follows.

The investigator must document any deviation from protocol procedures and notify the sponsor or contract research organization (CRO).

6.1. Subject Enrollment

Entry into screening does not guarantee enrollment into the study. In order to manage the total trial enrollment, Gilead, at its sole discretion, may suspend screening and/or enrollment at any site or trial-wide at any time.

6.1.1. Screening Visit

Subjects will be screened within 28 days before Day 1 visit to determine eligibility for participation in the study. The screening window can be extended up to 42 days for subjects in extenuating circumstances with sponsor approval. A single retest of screening labs is permitted only if there is reason to believe the retest value will be within accepted parameters if the initial value was due to a sample processing error or due to an extenuating circumstance such as an intercurrent infection.

The following will be performed and documented at screening:

- Obtain written informed consent
- Determine inclusion and exclusion eligibility
- Obtain medical history (refer to Section 6.7.2), including:
 - Hepatitis C treatment history, if applicable
 - Regimen (s)
 - Dates of previous treatment(s)
 - Response to previous treatment (i.e. nonresponder, relapse, discontinuation including reason)
- Complete physical examination (refer to Section 6.7.3)
- Obtain height and weight
- Obtain vital signs (refer to Section 6.7.4)

- Perform 12-Lead ECG (refer to Section 6.7.5)
- Record any serious adverse events and all adverse events related to protocol mandated procedures occurring after signing of the consent form.
- Obtain details of prior and concomitant medications
- Liver biopsy and/or Fibroscan results (if available)
- Diagnostic imaging (eg, ultrasound or CT scan, at the discretion of the Investigator) should

	be performed to exclude the presence of hepatocellular carcinoma (HCC). Imaging must be performed within 4 months of Day 1.
,	Obtain blood samples for tests:
	— Hematology
	— Chemistry
	— Coagulation tests
	— HCV RNA
	— Serum β-hCG pregnancy test for females of childbearing potential only
	 — Serum follicle stimulating hormone (FSH) (only for women of any age with amenorrhea of ≥ 12 months [refer to Appendix 4])
	— HCV Genotype
	 HCV antibody, HIV antibody, HBV surface antigen (HBsAg), HBV surface antibody (HBsAb), HBV core antibody (HBcAb)
	— HbA1c
	— Fibrotest®
,	Obtain urine sample for:
	— Urinalysis
	A single retest of Screening labs is permitted only if there is reason to believe the retest value

A single retest of Screening labs is permitted only if there is reason to believe the retest value will be within accepted parameters, for example, if the initial exclusionary value was either due to a sample processing error or due to an extenuating circumstance such as intercurrent illness.

Subjects meeting all of the inclusion criteria and none of the exclusion criteria will return to the clinic for enrollment into the study.

From the time of obtaining informed consent through the first administration of investigational medicinal product, record all serious adverse events (SAEs), as well as any adverse events related to protocol-mandated procedures on the adverse events case report form (eCRF). All other untoward medical occurrences observed during the screening period, including exacerbation or changes in medical history are to be captured on the medical history eCRF. See Section 7 Adverse Events for additional details.

6.1.2. Day 1 Assessments

An Interactive Web Response System (IWRS) will be employed to manage subject enrollment.

The following Day 1 tests and procedures must be performed prior to enrollment and dosing/dispensation of study drug:

- Determine inclusion and exclusion eligibility (refer to Sections 4.2 and 4.3)
- Perform complete physical examination (refer to Section 6.7.3)
- Obtain weight
- Obtain vital signs (refer to Section 6.7.4)
- Perform 12-Lead ECG (refer to Section 6.7.5)
- Assessment of AEs and concomitant medications
- Conduct pregnancy prevention counseling
- Obtain blood samples for tests:
 - Hematology
 - Chemistry
 - Coagulation tests
 - HCV RNA
 - IL28B Genotype
 - HCV resistance samples
- Obtain urine sample for:
 - Pregnancy test for females of childbearing potential only

When ready to administer study drug to the subject:

- Dispense study drug as directed by the IWRS
- Instruct the subject on the packaging, storage, and administration of study drug
- Instruct the subject on how to complete the subject diary
- Observe the subject taking the first dose of study drug.

6.2. Treatment Assessments (± 3 days)

On-treatment visits will be performed at the end of Weeks 1, 2, 4, 8, and 12 for all subjects.

Study drug will be reconciled at every post-Day 1 visit by the investigator in order to monitor the subject's adherence with the study drug.

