6.2.2. Week 2 (\pm 3 days)

The following procedures/assessments are to be completed at the end of Week 2:

- Obtain vital signs (refer to Section 6.7.4)
- Assessment of AEs and concomitant medications
- Assess adherence with study drug dosing regimen including pill count
- Obtain blood samples for tests:
 - Hematology
 - Chemistry
 - HCV RNA
 - HCV resistance samples
 - HBV DNA Sample

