3.7. Visit Windows

3.7.1. Definition of Study Day

Study day is the day relative to the date of the first dose of study drug. Study Day 1 will be defined as the day of first dose of study drug administration.

Study day will be calculated from the date of first dose of study drug administration and derived as follows:

- For postdose study days: Assessment Date First Dosing Date + 1
- For days prior to the first dose: Assessment Date First Dosing Date

The last dose date for the study drug will be the end date on study drug administration eCRF for the record where the "subject permanently discontinued" flag is 'Yes'.

If there are subjects for whom the date of last study drug is unknown due to the reason that the subject was lost to follow-up and not able to be contacted, the date of last dose will be estimated using the maximum of nonmissing study drug start or stop dates, visit dates, and laboratory collection dates (posttreatment visits and unscheduled visits are not included).

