3.7.2. Analysis Visit Windows

Subject visits might not occur on protocol-specified days. Therefore, for the purpose of analysis, observations will be assigned to analysis windows.

In general, the baseline value will be the last nonmissing value on or prior to the first dose date of study drug.

HCV RNA, vital signs, and safety laboratory data collected up to the last dose date + 3 days are considered to be on-treatment data and HCV RNA, vital signs, and safety laboratory data collected after the last dose date + 3 days are considered posttreatment data. The analysis windows for on-treatment HCV RNA, vital signs and safety laboratory data are provided in Table 1.

Table 1. Analysis Visit Windows for On-treatment HCV RNA, Vital Signs and Safety Laboratory Data

	HCV RNA	and Safety Labo	oratory Data	Vital Signs Data			
Nominal Visit	Nominal FU Day	Lower Limit	Upper Limit	Nominal FU Day	Lower Limit	Upper Limit	
Baseline	1	(none)	1	1	(none)	1	
Week 1	N/A	N/A	N/A	7	2	11	
Week 2	14	2	21	14	12	21	
Week 4	28	22	42	28	22	42	
Week 8	56	43	70	56	43	70	
Week 12	84	71	≥ 85	84	71	≥ 85	

HCV RNA, vital sign, and safety laboratory data collected after the last dose date + 3 days will be assigned to the posttreatment follow-up (FU) visit. Visit windows will be calculated from the last dose date (ie FU Day = collection date minus the last dose date) as shown in Table 2.

Table 2. Analysis Visit Windows for Posttreatment HCV RNA, Vital Signs and Safety Laboratory Data

		HCV RNA		Vital Signs and Safety Laboratory Dat			
Nominal FU ^a Visit	Nominal FU Day	Lower Limit	Upper Limit	Nominal FU Day	Lower Limit	Upper Limit	
FU-4	28	21	69	28	4	30	
FU-12	84	70	146	NA	NA	NA	
FU-24	168	147	210	NA	NA	NA	

a FU-x visit = posttreatment Week-x follow-up visit.

ECG data collected up to the last dose date + 3 days are considered to be on-treatment data. Qualitative assessments of whether the ECG is normal or abnormal will be assessed for on-treatment data based on the visit windows shown in Table 3.

Table 3. Analysis Visit Windows for On-treatment ECG Data

Nominal Visit	Nominal Day	Lower Limit	Upper Limit
Baseline	1	(none)	1
Week 12	84	2	(none)

Note: ECGs are to be collected at screening, baseline, Week 1, and Week 12 or Early Termination. For purposes of analysis, baseline value will be the last available value prior to the first dose of study drug and end of treatment value will be the last available value on or prior to the last dose date + 3 days.

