3.7.3. Selection of Data in the Event of Multiple Records in an Analysis Visit Window

Depending on the statistical analysis method, single values may be required for each analysis window. For example, change from baseline by visit usually requires a single value, whereas a time-to-event analysis would not require 1 value per analysis window.

If multiple valid, nonmissing measurements exist in an analysis window, records will be chosen based on the following rules if a single value is needed:

• For baseline, the last available record on or prior to the date of the first dose of study drug will be selected. If there are multiple records with the same time or no time recorded on the same day, the average (arithmetic mean) will be used for the baseline value. If multiple ECG measurements occur on the same day prior to first dose of any study drug, the average will be used as baseline for continuous data, regardless of the timing of these multiple ECG measurements.

b Days are calculated based on last dose date.

• For postbaseline values:

- The record closest to the nominal day for that visit will be selected except for HCV RNA
 posttreatment follow-up visits, for which the latest record in the analysis window will be
 selected.
- If there are 2 records that are equidistant from the nominal day, the later record will be selected.
- If there is more than 1 record on the selected day, the average will be taken, unless otherwise specified.
- If multiple valid nonmissing categorical observations exist in a window, records will be selected as follows:
 - For baseline, the last available record on or prior to the date of the first dose of study drug will be selected. If there are multiple records with the same time or no time recorded on the same day, the value with the lowest severity will be selected (eg, normal will be selected over abnormal). If multiple ECG measurements occur on the same day prior to the first dose of any study drug, the value with the lowest severity will be selected regardless of the timing of these multiple ECG measurements.
 - For postbaseline visits, follow the same rules described above for postbaseline numeric observations, except that if there are multiple records on the same day, the most conservative value will be selected (eg, abnormal will be selected over normal).

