4.2. Extent of Exposure

Extent of exposure to study drug will be examined by assessing the total duration of study drug exposure and the level of adherence to the study drug regimen specified in the protocol.

4.2.1. **Duration of Exposure to Study Drug**

Total duration of exposure to study drug will be defined as last dose date minus first dose date plus 1, regardless of any temporary interruptions in study drug administration, and will be expressed in weeks using up to 1 decimal place (eg, 4.5 weeks).

The total duration of exposure to study drug will be summarized using descriptive statistics (n, mean, SD, median, Q1, Q3, minimum, and maximum) and using the number of subjects (ie, cumulative counts) and percentage of subjects exposed through the following time periods: baseline (Day 1), Week 1 (Day 7), Week 2 (Day 14), Week 4 (Day 28), Week 6 (Day 42), Week 8 (Day 56), Week 10 (Day 70), and Week 12 (Day 84). A 3-day window is applied to the last planned on-treatment visit to match with the protocol-specified visit window, ie, the number of subjects exposed through Week 12 will be calculated as the number of subjects who were exposed to study drug for at least 81 days. Summaries will be provided for the Safety Analysis Set.

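### SAP Table 1 places a compliant Day 11 Week 2 vital-signs visit in the Week 1 window, so the reading is dropped from the by-visit summary or reported as Week 1

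*Protocol*

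**What the plan says.** Protocol Section 6.2 states that "On-treatment visits will be performed at the end of Weeks 1, 2, 4, 8, and 12 for all subjects". The tolerance is in the section heading: "6.2. Treatment Assessments (± 3 days". Protocol Section 6.2.2 then says "The following procedures/assessments are to be completed at the end of Week 2", and vital signs head the list that follows.

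The day numbers come from the SAP. Section 3.7.1 fixes the origin: "Study Day 1 will be defined as the day of first dose of study drug administration". Section 4.2.1 maps weeks to days as "baseline (Day 1), Week 1 (Day 7), Week 2 (Day 14), Week 4 (Day 28", and so on. Table 1 in Section 3.7.2, titled "Analysis Visit Windows for On-treatment HCV RNA, Vital Signs and Safety Laboratory Data", uses the same nominal days. Its first post-baseline row reads "Week 1 N/A N/A N/A 7 2 11": there is no Week 1 window for HCV RNA or laboratory data, and the vital-signs window is nominal Day 7 with limits 2 and 11. The Week 2 vital-signs window is nominal Day 14 with limits 12 and 21.

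Readings are assigned to visits by these windows. Where several fall in one window, SAP Section 3.7.3 says "The record closest to the nominal day for that visit will be selected", with ties going to the later record. SAP Section 7.3 plans a summary of vital signs and of change from baseline at each visit. Protocol Section 8.3 says missing vital signs are not imputed, apart from replacing a missing baseline with a screening value.

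**The concern.** An analysis window should at least contain every day on which the protocol allows the visit to take place. For vital signs at Week 2 it does not: the earliest allowed day, Day 11, belongs to Week 1 in Table 1. A site that follows the protocol exactly can therefore have its Week 2 reading removed from the by-visit table, or shown under the wrong week, with no deviation on its part.

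One clinic visit can also be split. HCV RNA and laboratory samples taken on Day 11 go to Week 2, because that window runs from Day 2 to Day 21, while the blood pressure and pulse taken at the same visit go to Week 1. At stake is the accuracy of a descriptive safety table, not any efficacy result.

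**Working it through.** **Inputs.** Tolerance of 3 days either way (Protocol 6.2). Vital-signs nominal days 7, 14, 28, 56 and 84, and vital-signs limits 2–11, 12–21, 22–42, 43–70 and 71 onward (SAP Table 1). Closest-record rule, ties to the later record (SAP 3.7.3).

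**Step 1: compliant days against windows.** Compliant days are the nominal day minus 3 to plus 3.

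| Visit | Compliant days | Table 1 window | All inside? |
|---|---|---|---|
| Week 1 | 4–10 | 2–11 | yes |
| Week 2 | 11–17 | 12–21 | no, Day 11 is outside |
| Week 4 | 25–31 | 22–42 | yes |
| Week 8 | 53–59 | 43–70 | yes |
| Week 12 | 81–87 | 71 onward | yes |

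Day 11 is the only compliant day that is misassigned.

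**Step 2: the other cuts in the table.** The midpoint between adjacent nominal days is (a + b)/2.

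| Pair | Midpoint | Upper limit in Table 1 |
|---|---|---|
| 7, 14 | 10.5 | 11 |
| 14, 28 | 21 | 21 |
| 28, 56 | 42 | 42 |
| 56, 84 | 70 | 70 |

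Three cuts equal the midpoint. The first exceeds it. Since |11 − 7| = 4 and |11 − 14| = 3, no nearest-day rule puts Day 11 in Week 1.

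**Step 3: what happens to a Day 11 reading.** It competes inside the Week 1 window at distance 4 from Day 7.

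- Week 1 visit on Days 4 to 10: its distance is 0 to 3, always less than 4. The Week 1 reading is selected, the Day 11 reading is used for no visit, and Week 2 is empty unless an unscheduled reading falls on Days 12 to 21.
- Week 1 visit on Day 3: distance 4, a tie. The later record, Day 11, is reported as Week 1.
- Week 1 visit on Day 2 (distance 5), or missed: the Day 11 reading is reported as Week 1.

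**Step 4: size.** There are 7 × 7 = 49 combinations of compliant Week 1 and Week 2 days. The 7 with Week 2 on Day 11 lose the Week 2 reading, and 7/49 = 14.3%. This counts combinations; it becomes a probability only if all allowed Week 2 days are equally likely, in which case 36/7 = 5.1 subjects are expected. The documents give no distribution of visit days. If visits cluster near Day 14, 0 to 2 subjects is a more plausible figure, again as an assumption.

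**Step 5: the corrected cut.** With Week 1 at Days 2–10 and Week 2 at Days 11–21, each compliant range in Step 1 lies wholly in its own window.

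**The case against.** The strongest counter-argument is that the limits are right and the nominal-day labels are off by one. The Protocol never gives Day 14 for Week 2. If sites schedule visits 7 and 14 days after Day 1, they fall on Days 8 and 15, with compliant ranges 5–11 and 12–18, and the 11/12 cut fits. The midpoints for Days 8, 15, 29, 57 and 85 are 11.5, 22, 43 and 71, which match all of Table 1's cuts if ties go to the later visit.

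As a reading of this SAP it fails. Table 1 prints 7 and 14 as the nominal days, and Section 4.2.1 repeats them. That section also applies the protocol's three-day tolerance to Day 84, counting exposure of at least 81 days as reaching Week 12. The same convention gives 14 − 3 = 11. What does stand is a practical caution: if sites did count from Day 8, moving the cut would transfer the edge case to a Day 11 Week 1 visit.

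It is also fair to say that analysis windows need not copy protocol windows and that the SAP states no midpoint rule. The problem does not depend on such a rule, however, because a compliant Week 2 visit is excluded from Week 2 either way.

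The points about importance stand in full. Vital signs are not an endpoint, SAP Section 7.3 rules out inferential statistics for them, and its by-subject listing keeps every reading.

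**Conclusion.** The Week 1/Week 2 limits for vital signs are wrong as written, given the SAP's own nominal days and the protocol's tolerance. The importance is minor. One calendar day is affected, in one descriptive table and its change-from-baseline companion. The number of subjects depends on how visits were spread: about 5 of 36 if evenly over the seven allowed days, 0 to 2 if clustered near Day 14. Both figures are assumptions, and zero is possible. SVR12, HCV RNA, laboratory and adverse-event results are untouched. The conclusion rests on Day 14 as the Week 2 target, which the SAP states twice and the Protocol only implies.

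**What to change.** In the vital-signs columns of SAP Table 1, change the Week 1 upper limit from 11 to 10 and the Week 2 lower limit from 12 to 11. Before doing so, confirm from the visit-scheduling instructions given to sites that Weeks 1 and 2 were targeted at Days 7 and 14. If they were targeted at Days 8 and 15, the nominal days are what need correcting instead.

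The cost is two numbers in one table and the matching lines of the windowing program. No new data are needed, and no efficacy or laboratory output changes.
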